6.2 DETAILS OF TRIAL PROCEDURES AT SELECTED VISITS

6.2.1 Screening period

After having been informed about the trial, all subjects will give their written informed consent in accordance with GCP and local legislation prior to enrolment in the study.

For information regarding laboratory tests (including drug and virus screening), ECG, vital signs, and physical examination, refer to Sections [5.2.3](#) to [5.2.5](#).

Pharmacogenomic genotyping will be performed in those volunteers whose genotypes are not known (for details see Section [5.3](#)).

6.2.2 Treatment periods

Study participants will be admitted to trial site at least 1 hour prior to administration of the trial medication. They will be kept under close medical surveillance for at least 24 hours following drug administration. Thereafter the subjects will be allowed to leave the trial site after formal assessment and confirmation of their fitness. Afterwards the study will be performed in an ambulatory fashion until the end-of-study examination.

For DGs 1-7 and 10 of the SRD part, each subject will receive one dose of the respective trial medication (BI 730357 or placebo) at visit 2. In DGs 8 and 9 of the SRD part, the same subjects will be included and each subject will be treated with the same trial medication (either always active or always placebo), i.e. they will receive the respective trial medication at first in DG 8 (Visit 2) following a standard continental breakfast and in DG 9 (Visit 3) following a high-fat breakfast. The treatments of DG 8 and DG 9 are separated by a wash-out phase of at least 14 days between each drug administration.

The participants of the BA part will receive the respective trial medication (BI 730357) at visit 2, 3 and 4. Details on treatments and procedures of administration are described in Section [4.1.4](#).

For details on time points and procedures for collection of plasma and urine samples for PK analysis, refer to [Flow Chart](#) and Section [5.5.2](#).

The safety measurements performed during the treatment period are specified in Section [5.2](#) of this protocol and in the Flow Chart. For details on time points for all other trial procedures, refer to the Flow Chart. AEs and concomitant therapy will be assessed continuously from screening until the end of trial examination.

6.2.3 End of trial period

For AE assessment, laboratory tests, recording of ECG and vital signs, and physical examination during the end of trial period, see Sections [5.2.2](#) to [5.2.5](#).

Subjects who discontinue treatment before the end of the planned treatment period should undergo the end of trial visit.

All abnormal values (including laboratory parameters) that are judged clinically relevant by the Investigator will be monitored using the appropriate tests until a return to a medically acceptable level is achieved. (S)AEs persisting after subject's end of trial must be followed up until they have resolved, have been sufficiently characterized, or no further information can be obtained.

The end of the trial as a whole is defined by the 'last regular visit completed by last subject' or 'end date of the last open AE' or 'date of the last follow-up test' or 'date of an AE has been decided as sufficiently followed-up', whichever is latest.

7. STATISTICAL METHODS AND DETERMINATION OF SAMPLE SIZE

7.1 STATISTICAL DESIGN – MODEL

7.1.1 Objectives

SRD Part:

The primary objective of the first (SRD) part of this trial is to investigate the safety and tolerability of BI 730357 by using descriptive statistics for all endpoints comparing active dose groups to placebo. The primary endpoint is defined in Section [5.2.1](#). Inferential statistics is not planned (as explained in Section [7.2](#)).

The secondary objective is the exploration of the pharmacokinetics (PK) of BI 730357. Endpoints as specified in [5.5.1](#) will be analysed by descriptive statistics. Secondary endpoints as defined in Section [5.5.1.1](#) will be subjected to analysis of dose proportionality by use of the power model.

BA Part:

The primary objective of the second part of the study is to investigate relative bioavailability of 25 mg BI 730357 as oral solution (Test 1, T1) and 25 mg BI 730357 given as tablet after a standardised high-fat breakfast (Test 2, T2), each compared to 25 mg BI 730357 as tablet in a fasting state (Reference, R)

The secondary objective is the evaluation and comparison of several PK parameters between the treatments. The secondary objectives will be assessed by descriptive statistics.

7.1.2 Endpoints

The primary endpoint to describe safety and tolerability of BI 730357 will be the number (%) subjects) with drug-related AEs. The collection of parameters pertaining to these investigations is described in detail in Section 5.2.1.

The secondary pharmacokinetic endpoints to be used for the assessment of dose proportionality and relative bioavailability are specified in Section 5.5.1.1.

7.1.3 Model

SRD part:

The basic model for the investigation of dose proportionality will be a power model that describes the functional relationship between the dose and PK endpoints.

$$\exp(Y_{ij}) = \alpha' * \exp(X_i)^\beta * \varepsilon'_{ij}$$

The model consists of a regression model applied to log-transformed data under fasting conditions. The corresponding ANCOVA model includes the logarithm of the dose as a covariate.

Proprietary confidential information © 2017 Boehringer Ingelheim International GmbH or one or more of its affiliated companies

Together with $\alpha' = \exp(\alpha)$ and $\varepsilon'_{ij} = \exp(\varepsilon_{ij})$, taking natural logarithms converts this model to a linear form as follows:

$$Y_{ij} = \alpha + \beta * X_i + \varepsilon_{ij}$$

where

Y_{ij}	logarithm of the pharmacokinetic endpoint for subject j at dose level i; where $i = 1, 2, \dots, 7, j = 1, 2, \dots, 8$;
α	intercept parameter;
β	slope parameter;
X_i	logarithm of dose i;
ε_{ij}	random error associated with subject j at dose level i (assumed to be independent and identically normally distributed).

This equation can be fit as a linear regression model. Based on the estimate for slope parameter (β), a 2-sided 95% CI for the slope will be computed. Perfect dose proportionality would correspond to a slope of 1. The assumption of a linear relationship between the log-transformed pharmacokinetic endpoint and the log-transformed dose will be checked.

If dose proportionality over the entire dose range investigated cannot be shown, an attempt will be made to identify dose range(s), where dose proportionality can be assumed.

BA part: Investigation of relative bioavailability

Relative bioavailability is primarily to be determined on the basis of the parameters $AUC_{0-\infty}$ and C_{max} (cf. [Section 5.5](#)). Those parameters will be ln-transformed (natural logarithm) prior to fitting the model.

The statistical model used for the analysis of $AUC_{0-\infty}$ and C_{max} will be an ANOVA (analysis of variance) model on the logarithmic scale. This model will include effects accounting for the following sources of variation: 'sequence', 'subjects within sequences', 'period' and 'treatment'. The effect 'subjects within sequences' will be considered as random, whereas the other effects will be considered as fixed. For tests on subject, period, and treatment effects, the denominator sum of squares will be the sum of squares for error; while for tests on sequence effects, the denominator will be the sum of squares for subjects. The model is described by the following equation

$$Y_{ijkm} = \mu + \zeta_i + s_{im} + \pi_j + \tau_k + e_{ijkm}, \text{ where}$$

Y_{ijkm} = logarithm of response (endpoint, see [Section 7.1.3](#)) measured on subject m in sequence i receiving treatment k in period j,

μ = the overall mean,

ζ_i = the ith sequence effect, $i = 1, 2, \dots, 6$

Proprietary confidential information © 2017 Boehringer Ingelheim International GmbH or one or more of its affiliated companies

s_{im} = the effect associated with the m^{th} subject in the i^{th} sequence,
 $m = 1, 2, \dots, n_i$

π_j = the j^{th} period effect, $j = 1, 2, 3$

τ_k = the k^{th} treatment effect, $k = 1, 2$

e_{ijkm} = the random error associated with the m^{th} subject in sequence i who received treatment k in period j .

The difference between the expected means for test treatments and reference treatment $\log(T_i) - \log(R)$, $i=1,2$, will be estimated by the difference in the corresponding Least Square Means (point estimate) and two-sided 90% confidence intervals based on the t-distribution will be computed. These quantities will then be back-transformed to the original scale to give the point estimator (geometric mean) and interval estimates for the ratio between response under test and response under reference.

Pairwise comparisons will be done for:

- Oral solution (PfOS) fasted (Test 1/T1) vs tablet fasted (Reference)
- Tablet fed (Test 2/T2) vs tablet fasted (Reference)

7.2 NULL AND ALTERNATIVE HYPOTHESES

Safety and tolerability of different dose groups of BI 730357 are to be determined on the basis of the investigated parameters in comparison to placebo. It is not planned to test any statistical hypotheses with regard to these variables in a confirmatory sense. Instead, they will be described in their entirety and evaluated by descriptive statistical methods.

In the SRD part, for the evaluation of dose proportionality, a two-sided 95% confidence interval (CI) of the slope will be computed. However, the CI will have to be interpreted in the perspective of the exploratory character of the study, i.e. as interval estimate for effects in the present data.

The relative bioavailability of BI 730357 will be estimated by the ratios of the geometric means (test/reference) for the secondary PK endpoints. Additionally, their two-sided 90% CIs will be provided. This method corresponds to the two one-sided t-tests procedure, each at the 5% significance level. Since the main focus is on estimation and not on testing, an acceptance range was not specified, that is, no hypothesis will be tested.

7.3 PLANNED ANALYSES

7.3.1 Primary analyses

Analysis of safety and tolerability is described in Section [7.3.3](#).

7.3.2 Secondary analyses

The secondary parameters (see Section [5.5.1](#)) will be calculated according to the relevant corporate procedure of the Sponsor ‘Standards and processes for analyses performed within Clinical Pharmacokinetics/Pharmacodynamics’ ([001-MCS-36-472](#), current version).

Pharmacokinetic parameters of a subject will be included in the analysis unless the subject has an important protocol violation relevant for the evaluation. Whether a protocol violation is important will be decided no later than in the Report Planning Meeting.

Reasons for exclusion of single pharmacokinetic parameters may be:

- The subject experiences emesis at or before two times median t_{max} . Median t_{max} is to be determined for the test product excluding the subjects experiencing emesis.
- The subject experiences emesis at any time during the labelled dosing interval.
- Time deviations
- Use of restricted medications

The subject set for the evaluation of PK endpoints (PKS) will include all treated subjects that provide at least one observation for at least one primary endpoint without important protocol violations with respect to the statistical evaluation of PK endpoints. It will also be decided in the Report Planning Meeting which subjects are to be included in the PKS.

Excluded subjects will be listed with their individual plasma concentrations and individual pharmacokinetic parameters, however, will not be included in descriptive statistics for plasma concentrations, pharmacokinetic parameters or other statistical assessment.

SRD Part: Assessment of dose proportionality

Dose proportionality of the secondary pharmacokinetic endpoints under fasting conditions will be explored based on the regression model described in Section [7.1.3](#). Based on the estimate for slope parameter (β), a 2-sided 95% CI for the slope will be computed. Perfect dose proportionality would correspond to a slope of 1. The assumption of a linear relationship between the log-transformed pharmacokinetic endpoint and the log-transformed dose will be checked.

If dose proportionality over the entire dose range under fasting conditions investigated cannot be shown, an attempt will be made to identify dose ranges, where dose proportionality can be assumed.

BA Part: Assessment of relative bioavailability

Point estimates of bioavailability, the ratios of the geometric means (test/reference) for the secondary endpoints (see [5.5.1.1](#)), and their two-sided 90% CIs will be provided.

To this end, the PK endpoints will be log transformed (natural logarithm) prior to fitting the ANOVA model (cf. Section 7.1.3). For each endpoint, the difference between the expected means for $\log(T_i) - \log(R)$ will be estimated by the difference in the corresponding adjusted means (LeastSquares Means), and a two-sided 90% confidence interval based on the t-distribution will be computed. These quantities will then be back-transformed to the original scale to provide the point estimate and 90% CIs for each endpoint.

7.3.3 Safety analyses

Safety analyses will be performed in accordance with BI standards.

All treated subjects (that is, all subjects who received at least one dose of study drug), will be included in the safety evaluation. Safety analyses will be descriptive in nature and will be based on BI standards.

Treatments will be compared in a descriptive way. The placebo control group in the safety evaluation will consist of all placebo treated subjects, regardless of the dose group in which they were treated. The active treatment groups will be compared to the placebo group in a descriptive way. Tabulations of frequencies/proportions will be used for the evaluation of categorical (qualitative) data, and tabulations of descriptive statistics will be used to analyse continuous (quantitative) data.

The analyses will be done by 'treatment at onset'.

Measurements (such as ECG, vital signs, or laboratory parameters) or AEs will be assigned to treatments (see Section [4.1](#)) based on the actual treatment at the planned time of the measurement or on the recorded time of AE onset (concept of treatment emergent AEs). Therefore, measurements planned or AEs recorded prior to first intake of trial medication will be assigned to 'screening', those between first trial medication intake until the end of trial visit will be assigned to the treatment period, and those after the end of trial examination will be assigned to 'post-study'. These assignments including the corresponding time intervals will be defined in detail in the TSAP.

Additionally, further treatment intervals (analysing treatments) may be defined in order to provide summary statistics for time intervals, such as combined treatments, on-treatment totals or periods without treatment effects (such as screening and post-study intervals).

Adverse events will be coded using the Medical Dictionary for Regulatory Activities (MedDRA). Frequency, severity and causal relationship of AEs will be tabulated by treatment, system organ class and preferred term. SAEs, AESIs (see Section [5.2.2.1](#)) and other significant AEs (according to ICH E3) will be listed separately.

Laboratory data will be compared to their reference ranges. Values outside the reference range as well as values defined as clinically relevant will be highlighted in the listings. Additionally, differences from baseline will be evaluated.

Vital signs or other safety-relevant data observed at screening, baseline, during the course of the trial and at the end-of-trial evaluation will be assessed with regard to possible changes compared to findings before start of treatment.

A centralised evaluation of all 12-lead ECGs recordings (see Section [5.2.4](#)) will be the basis for the derivation of further ECG parameters based on the ECG variables [REDACTED] [REDACTED]. The baseline value of an ECG variable is defined as the mean of the triple ECG measurements prior to drug administration. The derivation of the quantitative and qualitative ECG endpoints and their analyses will be described in the TSAP.

7.3.4 Preliminary PK analyses

A preliminary analysis of PK parameters (AUC_{0-24} and C_{max} of BI 730357) provided as individual values and geometric means of at least the first cohort per dose level, will be performed for

- all dose levels up to n-2 before proceeding to dose level n (with $n \leq 50$ mg)
- all dose levels up to n-1 before proceeding to dose level n (with $n > 50$ mg)

(Note: Data from the first cohorts of the above mentioned dose levels will be sufficient as long as the data from at least 2 subjects on active were available)

A preliminary analysis of pharmacodynamic biomarkers is not planned.

In contrast to the final PK/PD calculations, the preliminary analysis will be based on planned sampling times rather than on actual times, regardless of whether actual times were within the time windows or not. Therefore, minor deviations of preliminary and final results may occur. The preliminary analysis will provide individual and mean concentration/effect-time profiles and summary statistics of individual values without subject identification. The preliminary results will be distributed to the Investigator and the trial team.

Depending on preliminary data on safety, tolerability, changes of dosing schedule (e.g. additional intermediate doses) or planned times for PK/biomarker-sampling, additional preliminary PK-analysis may be performed based on the request of the trial clinical monitor, the Investigator, or trial clinical pharmacokineticist. Preliminary PK data will be distributed to the Investigator. No formal interim report will be written.

No inferential statistical preliminary analysis is planned. However, after each dose group the Investigator (or [redacted] deputy) is allowed to postpone further dose progression until a preliminary analysis of the data already obtained has been performed.

7.3.5 Pharmacokinetic analyses

The pharmacokinetic parameters listed in Section [5.5.1](#) for drug BI 730357 will be calculated according to the BI SOP ‘Standards and processes for analyses performed within Clinical Pharmacokinetics/Pharmacodynamics’ ([001-MCS-36-472](#)).

Subjects who are not included in the PKS (refer to Section [7.3.1](#)) will be reported with their individual plasma / urine concentrations and individual pharmacokinetic parameters; however, they will not be included in descriptive statistics for plasma / urine concentrations, pharmacokinetic parameters.

Only concentration values within the validated concentration range and actual sampling times will be used for the calculation of pharmacokinetic parameters. Concentrations used in the pharmacokinetic calculations will be in the same format provided in the bioanalytical report, (that is, to the same number of decimal places provided in the bioanalytical report).

If a predose concentration value is greater than 5% of C_{max} , the subject’s pharmacokinetic data will be not included in any statistical evaluations, in accordance with international guidances. The individual pharmacokinetic parameters of such a subject will be calculated and listed separately. If a predose concentration is above BLQ, but less than or equal to 5% of

Proprietary confidential information © 2017 Boehringer Ingelheim International GmbH or one or more of its affiliated companies

the subject's C_{max} value, the subject's data without any adjustments will be included in all pharmacokinetic measurements and calculations.

Every effort will be made to include all concentration data in an analysis. If not possible, a case to case decision is required whether the value should only be excluded from half-life estimation or the complete analysis.

- If a concentration is only excluded from half-life determination, it will be used for all other calculations (e.g. descriptive statistics) and for graphical presentation.
- If a concentration value is excluded from all calculations, it will not be presented graphically or used for the calculation of descriptive statistics and parameter determination. However the excluded concentration itself will be listed in the clinical trial report associated with an appropriate flag.

Descriptive statistics of parameters are calculated only when at least 2/3 of the individual parameter estimates of a certain parameter are available. If the actual sampling time will not be recorded or will be missing for a certain time point, the planned time will generally be used for this time point instead. Pharmacokinetic parameters which cannot be determined will be identified by "not calculated" (NC).

7.3.6 Biomarker analysis

7.3.6.1 Analysis of target engagement biomarkers

[REDACTED]

7.4 HANDLING OF MISSING DATA

7.4.1 Safety

With respect to safety evaluations, it is not planned to impute missing values.

7.4.2 Plasma drug concentration - time profiles

Handling of missing PK data will be performed according to the relevant SOP of the Sponsor ([001-MCS-36-472](#)).

Drug concentration data identified with NOS (no sample available), NOR (no valid result), NOA (not analysed), BLQ (below the lower limit of quantification), or NOP (no peak detectable) will be displayed as such and not replaced by zero at any time point (this rule also applies also to the lag phase, including the predose values).

7.4.3 Pharmacokinetic parameters

Handling of missing PK data will be performed according to the relevant SOP of the Sponsor ([001-MCS-36-472](#)).

For the non-compartmental analysis, concentration data identified with NOS, NOR or NOA will generally not be considered. Concentration values in the lag phase identified as BLQ or NOP will be set to zero. All other BLQ/NOP values of the profile will be ignored. The lag phase is defined as the period between time zero and the first time point with a concentration above the quantification limit.

7.5 RANDOMISATION

SRD part: Each dose group will be divided into two cohorts. The subjects of the first cohort will not be randomised to maintain a treatment sequence of active-placebo-active-active due to safety reasons. In the second cohort of each dose level the subjects will be assigned to active or placebo treatment using a 3:1 allocation ratio.

BA part: Subjects will be randomized to one of the six treatment sequences R/T1/T2, R/T2/T1, T1/T2/R, T1/R/T2, T2/T1/R, T2/R/T1 in a 1:1:1 ratio.

The Sponsor will arrange for the randomisation as well as packaging and labelling of trial medication. The randomisation list will be generated using a validated system, which involves a pseudo-random number generator and a supplied seed number so that the resulting allocation is both reproducible and non-predictable.

The randomisation list will contain additional blocks to allow for subject replacement (refer to [3.3.5](#)).

7.6 DETERMINATION OF SAMPLE SIZE

SRD part

It is planned to include a total of 72 subjects in this study part. The planned sample size is not based on a power calculation. The size of 8 subjects per dose group (6 on active treatment, and 2 on placebo) is commonly used in single-rising dose studies of the present type and is in general considered as sufficient for the exploratory evaluation of single dose safety and pharmacokinetics [[R95-0013](#)].

BA part

It is planned to enter 12 subjects in this trial part, because this sample size is considered sufficient to achieve the aims of this exploratory trial.

With this sample size, the following precision of the ratio of geometric means (test/reference) can be expected. Precision is defined as the ratio of upper to lower confidence interval limit. Note that the precision is independent of the actual ratio of geometric means. For this First-in-Man trial, no information on intra-subject variability is available. Therefore, Table [7.6: 1](#) provides an overview on the achievable precision for estimating the ratio of geometric means (test/reference) for three different gCV. For illustrative purposes, the expected 90% confidence intervals with 95% coverage probability are displayed for different values of geometric means ratios T/R in the three-period three-sequence crossover design.

Proprietary confidential information © 2017 Boehringer Ingelheim International GmbH or one or more of its affiliated companies

Table 7.6.1 Expected two-sided 90% confidence intervals for different gCVs and ratios T/R (N=12)

gCV[%]	Ratio ¹ [%]	Precision (upper CI limit/lower CI limit)	90% CI [%]
20	80	0.175	(67.17, 95.28)
	100	0.175	(83.97, 119.10)
	125	0.175	(104.96, 148.87)
	150	0.175	(125.95, 178.64)
	200	0.175	(167.93, 238.19)
25	80	0.217	(64.38, 99.41)
	100	0.217	(80.47, 124.27)
	125	0.217	(100.59, 155.33)
	150	0.217	(120.71, 186.40)
	200	0.217	(160.94, 248.53)
30	80	0.259	(61.74, 103.65)
	100	0.259	(77.18, 129.57)
	125	0.259	(96.47, 161.96)
	150	0.259	(115.77, 194.35)
	200	0.259	(154.36, 259.14)

1) Ratio of geometric means (test/reference) for a PL endpoint is defined by $\exp(\mu_T)/\exp(\mu_R)$

The expected 90% confidence interval limits in the table were derived by

$$CI\ limit_{upper,\ lower} = \exp(\ln(\theta) \pm \omega)$$

with θ being the ratio (T/R) on original scale and ω the distance from the estimate θ to either confidence interval limit on the log-scale, which was obtained from the achievable precision on the original scale.

The calculation was performed as described by [R12-0972] using R Version 3.0.3.

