Proprietary confidential information © 2017 Boehringer Ingelheim International GmbH or one or more of its affiliated companies

Number of global amendment	
	3
Description of change	
 Number of subjects in the SRD part increased by 16, administration of 400 mg and 800 mg BI 730357 or placebo under fed conditions added, option for additional subjects removed Visit 3 and standard breakfast added Preliminary clinical data on safety, tolerability and PK from the SRD and BA part presented 800 mg dose added, paragraph to 'maximum dose and dose escalation' amended Fasting conditions specified for SRD part Update on observed half-life Number of subjects increased, option for additional subjects removed, 3 additional dose groups (DGs) added in Table 3.3:1 No replacement for DGs 8, 9 and 10 Number of subjects increased, option for additional subjects removed DGs 8-10 added; maximum dose and number of dose cohorts adapted, DGs 8-10 added in Table 4.1.4: 1, high-fat breakfast and continental breakfast added in the SRD part, composition of standard continental breakfast added (Table 4.1.4:4) Treatments periods of DGs 8-9 described Investigation of dose proportionality under fasting conditions only Investigation of dose proportionality under fasting conditions only Number of subjects in the SRD part increased
Rationale for change	The highest exposures observed in this trial after the 400 mg dose under fasting conditions (C_{max} of 755 nM, AUC_{0-24} of 9,453 nM*h) are significantly below the predicted exposures at 400 mg (C_{max} of 2,547 nM and AUC_{0-24} of 42,458 nM*h) and the acceptable exposure limit of this trial (C_{max} of 5,920 nM, and AUC_{0-24} of 132,400 nM*h). Since we observed a 36% increase in exposure in the fed versus fasted condition, it is planned to investigate 3 additional DGs in the fed condition to further evaluate safety and PK of higher BI 730357 exposures, including the influence of food (normal and high-fat diet) on higher doses. The results will support the testing of higher exposures during the planned multiple-rising dose trial and further clinical development.

APPROVAL / SIGNATURE PAGE

Document Number: c11248385

Technical Version Number: 4.0

Document Name: clinical-trial-protocol-revision-03

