$$y_{km} = \mu + s_m + \tau_k + \varepsilon_{km},$$

where

y_{km} logarithm of response measured on subject m receiving treatment k ,
 μ the overall mean,
 s_m the effect associated with the m^{th} subject, $m = 1, 2, \dots, n$

τ_k the k^{th} treatment effect, $k = 1, 2$

e_{km} the random error associated with the m^{th} subject who received treatment k .

The difference between the expected means for test treatment (400mg high-fat breakfast) and reference treatment (400mg continental breakfast), $\ln(400\text{mg high-fat breakfast}) - \ln(400\text{mg continental breakfast})$, will be estimated by the difference in the corresponding Least Square Means (point estimate). Two-sided 90% confidence intervals based on the t-distribution will be computed. These quantities will then be back-transformed to the original scale to give the point estimator (geometric mean) and interval estimates for the ratio between response under test and response under reference.

The analysis will be accomplished by using the XPKISTAT macro, based on PKS (design BWU).

Investigation of relative bioavailability (BA part)

CTP: *Relative bioavailability is primarily to be determined on the basis of the parameters $AUC_{0-\infty}$ and C_{\max} [...]. Those parameters will be ln-transformed (natural logarithm) prior to fitting the model.*

The statistical model used for the analysis of $AUC_{0-\infty}$ and C_{\max} will be an ANOVA (analysis of variance) model on the logarithmic scale. This model will include effects accounting for the following sources of variation: 'sequence', 'subjects within sequences', 'period' and 'treatment'. The effect 'subjects within sequences' will be considered as random, whereas the other effects will be considered as fixed. For tests on subject, period, and treatment effects, the denominator sum of squares will be the sum of squares for error; while for tests on sequence effects, the denominator will be the sum of squares for subjects. The model is described by the following equation

$$y_{ijkm} = \mu + \zeta_i + s_{im} + \pi_j + \tau_k + e_{ijkm},$$

where

y_{ijkm} logarithm of response measured on subject m in sequence i receiving treatment k in period j ,

μ the overall mean,

ζ_i the i^{th} sequence effect, $i = 1, 2, \dots, 6$

s_{im} the effect associated with the m^{th} subject in the i^{th} sequence, $m = 1, 2, \dots, n_i$

π_j the j^{th} period effect, $j = 1, 2, 3$

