τ_k the k^{th} treatment effect, $k = 1, 2$ (Note: Separate models will be used to assess the difference between R and T1 and R and T2.)

e_{ijkm} the random error associated with the m^{th} subject in sequence i who received treatment k in period j .

[figure not shown]
The difference between the expected means for test treatments and reference treatment $\log(T_i)-\log(R)$, $i=1,2$, will be estimated by the difference in the corresponding Least Square Means (point estimate) and two-sided 90% confidence intervals based on the t-distribution will be computed. These quantities will then be back-transformed to the original scale to give the point estimator (geometric mean) and interval estimates for the ratio between response under test and response under reference.

[figure not shown]
Pairwise comparisons will be done for:

- *Oral solution (PfOS) fasted (Test 1/T1) vs tablet fasted (Reference)*
- *Tablet fed (Test 2/T2) vs tablet fasted (Reference)*

The analysis will be accomplished by using the XPKISTAT macro, based on PKS (design BWC).

In addition, a sensitivity analysis will be performed by fitting the model described above, but using all effects as fixed. This analysis will be done using PROC GLM.

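### Table 7.6:1 states 95% probability for limits that assume one joint model (20 error df); the SAP's separate pairwise models (9 df) meet them with about 81%, and the precision column prints log half-widths under a ratio heading

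*Protocol*

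**What the plan says.** **Protocol 7.6.** "It is planned to enter 12 subjects in this trial part", a number judged sufficient for exploratory aims rather than calculated. Because no within-subject variability was known, Table 7.6:1 shows the achievable precision for gCV 20, 25 and 30%. For illustration, "the expected 90% confidence intervals with 95% coverage probability are displayed" at five T/R ratios, for a three-period, three-sequence crossover. The text adds: "Precision is defined as the ratio of upper to lower confidence interval limit". The limits are computed as exp(ln θ ± ω), where ω is the distance from the estimate "to either confidence interval limit on the log-scale".

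**SAP 7.5.2 (BA part).** The model has sequence, subjects within sequences, period and treatment. The treatment index takes two values, and a note explains why: "Separate models will be used to assess the difference between R and T1 and R and T2". The error term is also stated: "For tests on subject, period, and treatment effects, the denominator sum of squares will be the sum of squares for error". Protocol 7.1.3 gives the same two-value treatment index but does not say that the models are separate.

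**Protocol 7.5.** "Subjects will be randomized to one of the six treatment sequences".

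SAP section 4 lists only the restriction of the dose-proportionality analysis as a change, and the SAP gives no revised precision.

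**The concern.** The width of a t-based interval, and how much that width varies from trial to trial, depend on the error degrees of freedom. A joint analysis of three treatments has far more of them than an analysis of two treatments at a time. If the table was built for the first and the plan specifies the second, its probability does not describe the intervals that will be reported. This table is the plan's only quantitative statement of what the BA part can deliver.

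The precision column raises a separate problem that needs no modelling. An upper limit divided by a lower limit cannot be below 1, yet every entry is.

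**Working it through.** **Inputs.** N = 12, two-sided 90% limits, 95% probability, gCV 20/25/30% (Protocol 7.6); six sequences (Protocol 7.5), taken as two subjects each, all evaluable; model effects and separate pairwise fits (SAP 7.5.2). The within-subject SD on the log scale is σ = √ln(1+gCV²) = 0.1980, 0.2462, 0.2936.

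**Error df and contrast variance, from the rank of the design matrix**

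| Model | Observations | Rank | Error df | Contrast variance / σ² |
|---|---|---|---|---|
| Joint (R, T1, T2) | 36 | 16 | 20 | 2/12 |
| R and T1 only | 24 | 15 | 9 | 2/12 |
| R and T2 only | 24 | 15 | 9 | 2/12 |

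Sequence is absorbed by subjects, so the joint count is 36 − (12 + 2 + 2) = 20 whether there are three or six sequences. Only the df differ between the models.

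**Half-width not exceeded with probability 95%**

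ω = t(0.95, df) · σ · √(2/12) · √(χ²(0.95, df)/df)

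*Reproducing the plan, 20 df.* t = 1.7247 and √(31.410/20) = 1.2532, product 2.1614. Multiplying by σ√(2/12) = 0.08085, 0.10052, 0.11985 gives ω = 0.1748, 0.2173, 0.2590. All 15 printed intervals then agree to two decimals. Neighbouring df do not fit: at gCV 20% and T/R 100% the upper limit is 119.25 with 19 df and 118.95 with 21 df, against 119.10 printed.

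*SAP models, 9 df.* t = 1.8331 and √(16.919/9) = 1.3711, product 2.5134. This gives ω = 0.2032, 0.2526, 0.3012, larger by 2.5134/2.1614 = 1.163.

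**Probability that a 9-df interval is no wider than printed.** The half-width with 9 df is 1.8331 · σ̂ · √(2/12). It stays within the printed value if 9σ̂²/σ² ≤ 9 · (2.1614/1.8331)² = 12.51. P(χ² with 9 df ≤ 12.51) = 0.814. Here σ cancels, so the result is the same at each gCV.

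**Average half-width** = t(0.95, df) · σ · √(2/12) · c4, where c4 = E(σ̂)/σ is 0.9876 for 20 df and 0.9727 for 9 df

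| gCV | 20 df | 9 df |
|---|---|---|
| 20% | 0.138 | 0.144 |
| 25% | 0.171 | 0.179 |
| 30% | 0.204 | 0.214 |

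The ratio is (1.8331 × 0.9727)/(1.7247 × 0.9876) = 1.047.

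**Precision column, from the printed limits at T/R = 100%**

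| gCV | Printed precision | Upper/lower | ln(upper/100) |
|---|---|---|---|
| 20% | 0.175 | 119.10/83.97 = 1.418 | 0.175 |
| 25% | 0.217 | 124.27/80.47 = 1.544 | 0.217 |
| 30% | 0.259 | 129.57/77.18 = 1.679 | 0.259 |

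The printed values are ω, not the ratio.

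**The case against.** The strongest reply accepts the arithmetic and disputes its weight. The table is offered as illustration, N = 12 does not come from it, and Protocol 7.2 sets no acceptance range and tests no hypothesis. The plan already admits that it does not know the variability: one step from gCV 20% to 25% raises ω by 24% (0.175 to 0.217), more than the 16% from the change in df. The correct limits stand beside the mislabelled column, so nobody is likely to misread the intervals. The printed limits are also right for a joint analysis of a three-period design, so the first part is a mismatch between table and analysis rather than a slip in calculation. On this view a corrected heading and a footnote giving the df would be enough.

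Much of that stands. It limits the consequence, and it is fair to call the first part an inconsistency. It does not remove the point. Uncertainty about gCV is shown openly in the table's rows, whereas the 95% is asserted within every row and is wrong for the planned models in all of them. Recomputing the table costs little more than footnoting it.

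A further objection is that 81.4% depends on assumptions. That is true. Separate fits may have different residual variances, and dropouts lower the probability: with 9 completers, 6 df and a contrast variance of 2/9 it would be about 53%.

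**Conclusion.** The point holds in both parts. The limits in Table 7.6:1 belong to a joint model with 20 error df. Under the SAP's pairwise models they are met with probability 81.4% instead of 95%, and the 95% log half-widths are 16% larger. The average interval is only 4.7% wider on the log scale. The precision column contradicts its own definition.

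The first part assumes 12 evaluable subjects and the same residual gCV in each pairwise model as in the joint one. It also reads the 95% as the probability that the half-width does not exceed ω. That reading is inferred from the match of all 15 rows, not from the cited method paper. The second part needs no assumption.

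The stated precision should be corrected, but neither the sample size nor any decision rule depends on it. The reference to three sequences is an editorial error and does not alter the 20 df.

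**What to change.** Restate Table 7.6:1 for the pairwise models (9 df, 95% probability on the half-width):

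| T/R | gCV 20% | gCV 25% | gCV 30% |
|---|---|---|---|
| 80% | 65.29–98.03 | 62.14–102.99 | 59.19–108.12 |
| 100% | 81.61–122.53 | 77.67–128.74 | 73.99–135.15 |
| 125% | 102.01–153.17 | 97.09–160.93 | 92.49–168.94 |
| 150% | 122.42–183.80 | 116.51–193.11 | 110.99–202.73 |
| 200% | 163.22–245.07 | 155.35–257.48 | 147.98–270.30 |

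In the precision column, either print the ratios exp(2ω) = 1.50, 1.66 and 1.83, or relabel it as the half-width on the log scale and print 0.203, 0.253 and 0.301; make the definition in the text agree. State the two assumptions (equal residual gCV, 12 evaluable subjects) and change three-sequence to six-sequence.

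Leave the pairwise models and N unchanged. The log for amendment 3 records "Preliminary clinical data on safety, tolerability and PK from the SRD and BA part presented", so BA results were already known and the model should not be altered to fit the table.

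The cost is an edit to text and table, and a somewhat less favourable stated precision. Nothing changes for subjects, sample size or analysis.
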